6.7.6 Monitoring of subjects with adverse events

Any AE that occurs in the course of the clinical study must be monitored and followed up until the end of study visits. It is the responsibility of the investigator that any necessary additional therapeutic measures and follow-up procedures are performed.

6.7.7 Overdose

In case of a significant overdose of a study drug, this has to be reported as a serious adverse event.

7 DATA MANAGEMENT UND STATISTICAL ASPECTS

7.1 DATA MANAGEMENT

All data will be recorded in a computer database system. Data entry will be performed twice by at least two persons independently. The double entry will be validated and cross-checked by a computer programme.

The following software systems will be used:

S-PLUS by Insightful Corp., Seattle, USA

Report/Testimate/N/Nsurv der Fa. IDV, Gauting

VisualFoxpro für Windows von der Fa. Microsoft, Redmond, USA

Patients will be informed that data on their disease and its course will be stored in an pseudonymized way. Each patient has the right to know which information has been stored electronically.

7.2 BIOSTATISTICAL ASPECTS

7.2.1 General design

The present trial is designed as a phase I/II study which aims at estimating the feasibility of the combined modality regimen consisting of chemoradiation including 5-FU/oxaliplatin and deep regional hyperthermia. The feasibility rate, i.e. the rate of patients without DLT (according to the definition in section XXX) *or* premature radiochemotherapy treatment withdrawal *or* hyperthermia delivery < 80%, is chosen as primary efficacy endpoint.

The estimation of the feasibility rate is to be based on an explorative pilot study, since immediate embarking on a large scale comparative efficacy trial would not be acceptable from the point of view of resources. Moreover, this would induce ethical objections, as it does not seem to be justifiable to expose a large number of patients to an experimental approach without any exploratory indications of an improved risk-benefit ratio.

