11.5 Registration and request for authorisation of the trial	
11.6 Ethical committee	
11.7 Protocol amendments	
11.8 Subject insurance	
11.9 Information on study drugs to trial investigators	
12 REFERENCES	49

APPENDICES

- 1 RECIST Criteria
- 2 Performance status scale (ECOG)
- 3 NCI CTCAE V. 3
- 4 Patient information
- 5 Patient informed consent form
- 6 Fachinformationen (SmPC)
- 7 Declaration of Helsinki
- 8 CRF
- 9 Ethical committee approval
- 10 (Request for) authorisation (BfArM)
- 11 Subject insurance

STUDY SYNOPSIS

Protocol title	Neoadjuvant chemoradiation with 5-FU and oxaliplatin combined with deep regional hyperthermia in locally recurrent rectal cancer (HyRec-Trial)
Study design / phase	Multi-institutional phase II study
Objective of the study	To decide upon the feasibility of a multimodal regimen consisting of radiochemotherapy and hyperthermia
Primary endpoints	 Feasibility rate (i.e. rate of patients not experiencing dose- limiting toxicity [DLT])
	Number of hyperthermia applications by patient
Secondary endpoints	Local progression-free survival
	Distant metastasis-free survival
	Overall survival
	Response rate (RECIST criteria)
	Rate of curative resections (R0)
	 Rate of acute and late toxicity according to NCI CTC, and postoperative morbidity

Flow chart

Inclusion Criteria	• Age ≥ 18 years
	 Life expectancy ≥ 2 years
	 Histologically confirmed locally recurrent (resectable or non-resectable) adenocarcinoma of the rectum
	 ECOG-performance status < 2
	Sufficient bone marrow function:
	WBC > 3,5 x 10 ⁹ /l Neutrophil granulocytes > 1,5 x 10 ⁹ /l Platelets > 100 x 10 ⁹ /l Hemoglobin > 10 g/dl
	Sufficient liver function:
	Bilirubin < 2,0 mg%
	SGOT, SGPT, alkaline phosphatase, gGT less than 3 times upper limit of normal
	 Serum creatinine < 1,5 mg%, glomerular filtration rate > 50 ml/min
	Signed study-specific consent form prior to therapy
	 Fertile patients must use effective contraception during and for 6 months after study treatment
	 Considered fit for oxaliplatin and 5-FU containing combination chemotherapy.
Exclusion criteria	Pelvic radiotherapy during the last 12 months
	Pregnant or lactating/nursing women
	Distant metastasis (M1)
	Drug addiction
	On-treatment participation on other trials
	Active intractable or uncontrollable infection

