2 STUDY OBJECTIVES

2.1 **PRIMARY OBJECTIVE**

Primary objective of the study is to decide upon the feasibility of the combined modality regimen consisting of chemoradiation including 5-FU/oxaliplatin and deep regional hyperthermia by assessment of the rate of patients without dose-limiting toxicity (DLT). In addition, the number of applied hyperthermia treatments by patient will be determined.

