6.7 CRITERIA FOR SAFETY EVALUATION

6.7.1 Dose-limiting toxicity (DLT)

The following adverse reactions are defined as dose-limiting toxicity in the context of the **primary objective** of the trial to determine the feasibility rate (cf. section 7.2):

- Leukopenia or neutropenia of severity grade 3 or 4 with complications such as fever (> 38,5°C) or infection, or with a duration of > 7 days
- Thrombocytopenia of grade 3 or 4
- Non-hematological toxicity of grade 3 or 4 (except for nausea)
- Each toxicity leading to permanent discontinuation of at least one of the drugs or other treatment modalities, except for hyperthermia, if more than 60% of the scheduled applications occurred, or a delay of treatment of more than 3 weeks

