7.2.2 Sample size calculation

The main objective of the trial is to assess, whether radiochemotherapy plus hyperthermia shows a promising feasibility profile in the treatment of locally recurrent rectal cancer. The primary endpoint is the feasibility rate as defined in section 7.2.1.

Conventional empirical phase I study designs in clinical oncology assume, that an antineoplastic treatment is not feasible, if an unacceptable toxicity occurs in more than 1 out of 3 or 4 patients; however, the occurrence of dose limiting toxicities (DLT) in 1/6 is accepted^{32,33,34,35}. This leads to the conclusion that the limit of acceptance is considered to be around 20% in medical cancer treatment.

In order to (from an ethical point-of-view) prevent to treat an unnecessarily high number of patients with a treatment regimen that is practically not feasible, a two-stage design according to SIMON (1989) will be applied. This allows for the termination of the study with a relatively low patient number in case of a definitely not acceptable feasibility rate. If this first step is passed without termination, further recruitment occurs in a second stage, in order to be able to ascertain a promising level of feasibility, hence qualifying the experimental treatment for further evaluation or application.

In summary, the trial design is based on the following assumptions:

- The experimental therapy would be rated as unacceptable, if the actual feasibility rate (= 1 withdrawal/DLT rate) was 70 % or lower.
- On the other hand, the multimodal regimen would be considered to be a promising candidate for further development (e.g. in a phase III trial), if the true feasibility rate amounted to 85% or more.
- Probability to accept the experimental therapy as well tolerable, in spite of a *true* feasibility rate of < 70% (i.e. withdrawal/DLT rate > 30%): 5% (type I error)
- Probability to reject the experimental therapy as not sufficiently feasible (<70%), although the *true* feasibility rate is promising (> 85%): 20% (type II error, corresponding to a power of 80%).

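### The primary feasibility rate is DLT-free only in the synopsis and section 2.1, but a wider composite with withdrawal and hyperthermia delivery in section 7.2.1

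*Protocol*

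**What the plan says.** The definition appears in four places.

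- **Synopsis, primary endpoints.** The feasibility rate is the "rate of patients not experiencing dose- limiting toxicity [DLT"; the number of hyperthermia applications per patient is listed as a separate item.
- **Section 2.1.** Feasibility is to be decided "by assessment of the rate of patients without dose-limiting toxicity (DLT"; the number of hyperthermia treatments is determined in addition.
- **Section 7.2.1.** The rate covers patients "without DLT (according to the definition in section XXX", a placeholder that was never filled, and who also have neither premature radiochemotherapy withdrawal nor low hyperthermia delivery: "hyperthermia delivery < 80%, is chosen as primary efficacy endpoint".
- **Section 7.2.2.** "The primary endpoint is the feasibility rate as defined in section 7.2.1". The first design assumption then calls the regimen unacceptable "if the actual feasibility rate (= 1 withdrawal/DLT rate) was 70 % or lower", which has no hyperthermia term.

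Two further sections bear on this. Section 6.7.1 defines DLT and refers to 7.2 for the feasibility rate. Among its criteria is toxicity that ends a modality for good, "except for hyperthermia, if more than 60% of the scheduled applications occurred". Section 7.2.3 removes and replaces patients who leave treatment within the first two cycles for reasons clearly unrelated to toxicity.

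**The concern.** The 70% and 85% hypotheses, the 5% and 20% error rates and the stage-1 stopping rule all describe one yes/no outcome per patient. If the objectives and the statistical section classify some patients differently, the protocol does not say unambiguously who counts as a failure at the stage-1 look. A choice between the readings made after the data are known would weaken the pre-specification behind the stated error rates. The patients affected are those in whom the experimental modality was under-delivered or radiochemotherapy ended early without a DLT. In a feasibility trial these are not a side issue.

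**Working it through.** **Inputs from the protocol.** Section 7.2.2 gives p0 = 0.70, p1 = 0.85, type I error 5%, power 80%, 19 patients in stage 1, rejection at 5 or more non-feasible (14 or fewer feasible), and 59 in total. Section 5.4.1 gives 10 scheduled sessions. Section 7.2.5 states a different patient count for the interim analysis. That is a separate matter; 19 is used here because it belongs to the printed stopping rule.

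**Inputs not in the protocol.** These are the final cut-off and the discordant share d, meaning patients who succeed under DLT-only and fail under 7.2.1, in percentage points of all patients. A range of 2 to 15 is assumed for d.

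**1. The plan's own design.** With at least 15/19 needed to continue and at least 47/59 to accept,

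P(accept | p) = Σ over x = 15 to 19 of P(Bin(19, p) = x) × P(Bin(40, p) ≥ 47 − x).

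An exact search for the smallest expected sample size under p0 returns 14/19 and 46/59 as the largest failing counts. Type I error is 0.0494, power 0.8067 and early stopping at p0 0.718. Expected size at p0 is 19 + (1 − 0.718) × 40 = 30.3. The printed 19, 5 failures and 59 are reproduced, so the sample size is correct.

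**2. Classifying patients who have no other DLT and complete radiochemotherapy.**

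| Hyperthermia given | Synopsis and 2.1 | 7.2.1 |
|---|---|---|
| 8 to 10 of 10 | success | success |
| Stopped for toxicity after 7 (70%: above 60%, below 80%) | success | failure |
| Stopped for toxicity after 6 or fewer | failure (DLT) | failure |
| 7 or fewer, non-toxicity reasons | success | failure |

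Seven is the only count between the two thresholds. The wider gap is the last row. A DLT-free patient who withdraws early from radiochemotherapy is also discordant, unless 7.2.3 replaces that patient.

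**3. One patient at stage 1.** With 4 failures in 19 under DLT-only, the trial continues. One discordant patient makes it 5 in 19 under 7.2.1, and the regimen is rejected. This step uses only printed text.

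**4. Size, for assumed d.** Success under 7.2.1 implies success under DLT-only. The difference between the two acceptance probabilities is therefore the chance that the same data give opposite final decisions. With 85% DLT-free, the DLT-only reading stops at stage 1 with probability 14.4% and accepts with probability 80.7%.

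| d | Rate under 7.2.1 | Stage-1 stop, 7.2.1 | P(accept), 7.2.1 | Opposite decisions |
|---|---|---|---|---|
| 2 | 83% | 21.1% | 69.5% | 80.7 − 69.5 = 11.2% |
| 5 | 80% | 32.7% | 49.5% | 31.2% |
| 10 | 75% | 53.5% | 19.7% | 61.0% |
| 15 | 70% | 71.8% | 4.9% | 75.8% |

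**5. The converse.** If the true 7.2.1 rate is 70%, the DLT-only rate is 72, 75, 80 or 85% for the same d. Judged on DLT-only, the regimen is accepted with probability 9.1, 19.7, 49.5 or 80.7%, instead of the planned 5%.

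**The case against.** The strongest reply is that the endpoint is settled. Section 7.2.2 names the 7.2.1 definition outright, and the hypotheses, error rates and stage-1 rule sit in that section. Section 6.7.1 defines only DLT and itself points to 7.2. On this view the withdrawal/DLT wording in the 7.2.2 assumptions is loose shorthand, and the synopsis and 2.1 are abbreviations. Much of this stands: 7.2.1 has the best claim to govern, and 7.2.2 is not an independent third endpoint. It does not remove the conflict. The synopsis and the primary objective state a different success criterion, and the stated null hypothesis omits the delivery term.

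A reader might infer that 60% and 80% are rival cut-offs. They are not. The 60% is an exemption inside the DLT component and the 80% is a separate delivery component; within 7.2.1 both can hold, and the patient with 7 sessions simply fails on delivery.

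A second reply is that the final decision is a judgement. Section 7.2.2 bases it on the rate, its confidence interval, treatment delivery and toxicity, and prints no final cut-off. That is right, and it limits the final acceptance figures to an illustration. The protocol's own table gives 69 to 88% for 47/59, so a rule requiring the lower limit to exceed 70% would not accept that result. The stage-1 rule, however, is a plain count.

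**Conclusion.** The inconsistency is real and should be removed before patients are classified for the stage-1 decision. It lies between the synopsis and 2.1 on one side and 7.2.1 on the other, with the 7.2.2 assumptions matching neither exactly. That a single discordant patient can reverse the stage-1 decision follows from the printed rule. The stage-1 probabilities depend on the assumed d; the acceptance probabilities depend on d and also on the derived cut-off of at least 47/59. At d = 2 the change is moderate (81% to 70%, or 5% to 9% in the converse case); at d = 10 it is large (81% to 20%, or 5% to 49%).

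Two stronger conclusions are not supported. A reader might infer that the 5% type I error has no meaning; but 7.2.2 names an endpoint for it, so pre-specification is weakened rather than absent. A reader might also infer that the objectives ignore under-delivery; but the synopsis and 2.1 both record the number of sessions, and 7.2.2 weighs it in the final conclusion. Delivery is missing from the DLT-only rate, not from the trial.

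**What to change.** - Use the 7.2.1 composite, which 7.2.2 already names, word for word in the synopsis, in 2.1 and in the 7.2.2 design assumptions.
- Replace the placeholder section number in 7.2.1 by 6.7.1.
- Report the DLT-free rate and the number of hyperthermia sessions as separate descriptive components.
- State that the 60% in 6.7.1 is an exemption within the DLT component and the 80% in 7.2.1 a separate delivery component. The sponsor should reconcile the two passages; no threshold is proposed here.
- Reconcile the withdrawal term in 7.2.1 with the replacement rule in 7.2.3, so that it is clear which early withdrawals are failures and which are replaced.

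The cost is protocol wording. The design stays at 19 and 59, because these depend only on p0, p1 and the error rates. The downside is that the observed rate may be slightly less favourable than a DLT-only rate.

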7.2.2 Sample size calculation

The main objective of the trial is to assess, whether radiochemotherapy plus hyperthermia shows a promising feasibility profile in the treatment of locally recurrent rectal cancer. The primary endpoint is the feasibility rate as defined in section 7.2.1.

Conventional empirical phase I study designs in clinical oncology assume, that an antineoplastic treatment is not feasible, if an unacceptable toxicity occurs in more than 1 out of 3 or 4 patients; however, the occurrence of dose limiting toxicities (DLT) in 1/6 is accepted^{32,33,34,35}. This leads to the conclusion that the limit of acceptance is considered to be around 20% in medical cancer treatment.

In order to (from an ethical point-of-view) prevent to treat an unnecessarily high number of patients with a treatment regimen that is practically not feasible, a two-stage design according to SIMON (1989) will be applied. This allows for the termination of the study with a relatively low patient number in case of a definitely not acceptable feasibility rate. If this first step is passed without termination, further recruitment occurs in a second stage, in order to be able to ascertain a promising level of feasibility, hence qualifying the experimental treatment for further evaluation or application.

In summary, the trial design is based on the following assumptions:

- The experimental therapy would be rated as unacceptable, if the actual feasibility rate (= 1 withdrawal/DLT rate) was 70 % or lower.
- On the other hand, the multimodal regimen would be considered to be a promising candidate for further development (e.g. in a phase III trial), if the true feasibility rate amounted to 85% or more.
- Probability to accept the experimental therapy as well tolerable, in spite of a *true* feasibility rate of < 70% (i.e. withdrawal/DLT rate > 30%): 5% (type I error)
- Probability to reject the experimental therapy as not sufficiently feasible (<70%), although the *true* feasibility rate is promising (> 85%): 20% (type II error, corresponding to a power of 80%).

According to these parameters, and using the variant out of the class of optimal twostage designs by SIMON (1989) that leads to the lowest expected number of patients required in case of true non-feasibility, $\mathbf{n} = 19$ patients evaluable for feasibility have to be recruited in the first stage. The combination will be rejected, if five or more of these patients fulfil the criterion of non-feasibility. In the second step, further patients will be recruited up to a total number of **59 evaluable cases**. The final conclusion of the trial will depend on the definite feasibility rate (and its confidence interval), the achieved level of treatment delivery (especially, the number of hyperthermia applications) as well as the complete information on type, frequency and severity of toxicities.

The precision of the estimation of the feasibility rate in the respective arms/strata is provided by confidence intervals in the following table, for different actual feasibility rate findings:

Feasibility rate	exact 90% confidence interval		
41/59 (≈70%)	58 79 %		
47/59 (80%)	69 88 %		
53/59 (90%)	81 95 %		

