7.2.5 Interim and final analyses

As described and justified in 7.2.2, an interim analysis is performed, when 10 patients are evaluable for feasibility.

The main biometrical evaluation of the study and the compilation of the statistical report as part of the integrated clinical/biometrical report will be performed six months after termination of patient recruitment as well as after completion and/or correction of all case report forms. An additional analysis on long-term results will be performed 5 years later.

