The investigator is obliged to complete the case report forms within a reasonable time period after retrieval of the data (i.e. usually within 2 weeks). The completed forms are signed by the investigator, where necessary. The original has to be sent to the data management office or handed over to the monitor in case of on-site visits. A copy remains with the investigator. The study office or monitor checks the forms for completeness and plausibility. In case of queries, the form or a photocopy of it will be sent or given back to the investigator for clarification/correction/ completion. Queries have to be handled within 4 weeks.

After finalisation of the data checks by the study office/monitor the originals or fair copies are sent to the biostatistical center. If additional queries arise there during computer data entry, they are handled by the investigator via monitor or study office contacts.

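### Five failures among the first 19 patients already decide stage 1, but the protocol names only patient counts as decision points and gives no prompt route for counting failures that are not SAEs

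*Protocol*

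**What the plan says.** Section 7.2.2 adopts a Simon two-stage design, giving as its ethical reason the wish to "prevent to treat an unnecessarily high number of patients with a treatment regimen that is practically not feasible". The regimen is unacceptable at a feasibility rate of 70% or lower and promising "if the true feasibility rate amounted to 85% or more". Type I error is 5% and power 80%. The variant chosen is the one "that leads to the lowest expected number of patients required in case of true non-feasibility". Stage 1 has 19 evaluable patients and the full trial 59. The stage-1 rule is: "The combination will be rejected, if five or more of these patients fulfil the criterion of non-feasibility".

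Section 7.2.5 says: "As described and justified in 7.2.2, an interim analysis is performed". It sets that analysis at 10 evaluable patients, although the section it cites gives 19.

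Section 5.9 lets the sponsor or coordinating investigator end the trial at any time, especially for severe or frequent adverse events. It gives no number and does not mention the five-failure rule.

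On reporting, sections 5.7 and 6.7.5 require SAEs to reach the coordinating investigator within 24 hours. Other adverse events are recorded on the CRF toxicity form (6.7.2). For the CRF, section 8.1 states: "The investigator is obliged to complete the case report forms within a reasonable time period after retrieval of the data". This usually means 2 weeks, and queries are to be handled within 4 weeks.

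**The concern.** The rule is an absolute count. Once five of the first 19 evaluable patients have failed, at most 14 can be feasible, and no later stage-1 patient can reverse the rejection. The protocol does not tie any action to that moment. It describes no running count, no stop at the fifth failure and no pause in recruitment while a look is awaited.

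The information needed for such a count is also not assured. Under 6.7.1 and 7.2.1, a patient can be non-feasible through some grade 3 toxicities, hyperthermia delivery below 80%, or premature withdrawal from radiochemotherapy. None of these is necessarily an SAE. The coordinating investigator may therefore not know promptly that the fifth failure has occurred.

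At stake is the aim that 7.2.2 itself gives for the two-stage design. Patients may be enrolled on a regimen whose stage-1 rejection is already settled, and this is more likely the less feasible the regimen is.

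**Working it through.** **Inputs.** From 7.2.2: p0 = 0.70, p1 = 0.85, type I error 0.05, power 0.80, stage 1 of 19, rejection at 5 or more failures, total 59. From 7.2.5: a look at 10. From 3.3: recruitment July 2008 to June 2010, so 24 months. From 6.3: end of radiochemotherapy at day 35.

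**1. The plan's own design.** An exact binomial search over two-stage designs with total size 40 to 74 minimised expected size at p0, subject to the two error limits. The optimum is 14/19 and 46/59: reject in stage 1 at 14 or fewer feasible of 19, and at the end at 46 or fewer of 59. Section 7.2.2 does not print the final cut-off of 46; it comes from this search. Results:
- Type I error 0.0494 and power 0.8067.
- Probability of stage-1 rejection 0.718 at 70% and 0.144 at 85%.
- Expected size at 70%: 19 + (1 − 0.718) × 40 = 30.3.

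The stated 19, 5 and 59 are reproduced.

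**2. Stopping at the fifth failure.** Let p be true feasibility, q = 1 − p, and K the number of the patient who is the fifth failure. Then P(K = k) = C(k − 1, 4) q^5 p^(k − 5), for k = 5 to 19. K is at most 19 exactly when there are five or more failures among 19. The stage-1 decision is therefore the same under either rule, and so are type I error and power.

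**3. Patients spared, given rejection.** If m further patients are already enrolled when the fifth failure becomes known, the saving against a look at 19 is the mean of 19 − min(19, K + m), given K ≤ 19.

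For m, planned accrual is 59/24 = 2.46 patients per month. Over 35 days this gives 2.46 × 35/30.4 = 2.8, so about 3 patients on treatment at once.

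If the five-failure rule is also applied at 10 patients, the comparator is 10 + m when K ≤ 10, and 19 otherwise.

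| True feasibility | P(reject in stage 1) | P(K < 19) | Mean K given rejection | Saving, m = 0 | Saving, m = 3 | Saving, m = 3, rule also applied at 10 |
|---|---|---|---|---|---|---|
| 70% | 0.718 | 0.667 | 13.55 | 5.45 | 2.90 | 1.64 |
| 60% | 0.930 | 0.906 | 11.75 | 7.25 | 4.44 | 2.08 |
| 50% | 0.990 | 0.985 | 9.89 | 9.11 | 6.16 | 2.39 |

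The m = 0 column is 19 minus the mean of K. For example, 19 − 13.55 = 5.45.

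At 70% with m = 1 to 5, the saving is 4.52, 3.67, 2.90, 2.23 and 1.65. Not conditioning on rejection, the m = 0 saving at 70% is 0.718 × 5.45 = 3.9, so expected size falls from 30.3 to 26.4.

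**4. The look at 10.** Five failures are present by patient 10 with probability 0.150 at 70%, 0.367 at 60% and 0.623 at 50%. At 70% this compares with 0.718 by patient 19. A look at 10 alone does not carry out the 5-of-19 rule.

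**The case against.** Judging stage 1 at its full size is the ordinary Simon procedure, and the protocol computes that design correctly. A reader might infer that the error rates or sample size are wrong. They are not, and counting failures as they occur is a refinement.

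A reader might also infer that the protocol obliges sites to go on enrolling after the fifth failure. It does not. The sentence in 7.2.2 does not make rejection wait for patient 19, no section requires further enrolment, and 5.9 permits a stop at any time. What remains is that an earlier stop is permitted but not fixed.

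It would be too strong to say that DLTs have no fast route. Section 6.7.3 lists blood dyscrasias without hospitalisation among events usually to be considered serious, life-threatening events are SAEs, and severe diarrhoea leads to hospitalisation under 5.6.3. Many DLTs will therefore be reported within 24 hours. The gap is limited to other grade 3 events, hyperthermia shortfall and premature withdrawal.

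Nor do the 2 and 4 weeks in 8.1 add up to a six-week delay before the study office hears of an event. The form arrives first and queries follow.

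Finally, the larger savings assume that no look takes place before 19. If the rule is applied at 10 as well, a fifth failure at patient 9 would be acted on one evaluable patient later, and the saving shrinks as the table shows.

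Running-count mechanics could be placed in a document not shown here. However, when enrolment stops and what sites must notify are conduct rules that investigators need to find in the protocol.

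**Conclusion.** The point stands as an inexpensive improvement and not as a fault in the design calculation. The protocol has a decisive count of five but attaches decisions only to patient numbers, and those numbers disagree (19 against 10). Non-SAE failures may not be known promptly.

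Given stage-1 rejection, acting at the fifth failure spares on average between about 1.6 and 5.4 patients at 70% true feasibility. At 60% the range is about 2.1 to 7.25, and at 50% about 2.4 to 9.1. The upper ends assume that every outcome is known at once and that the only look is at 19. The lower ends assume three patients already on treatment and the rule applied at 10 as well. All figures assume independent outcomes with a common feasibility rate. The three-patient overrun is an assumption drawn from planned accrual and treatment length; actual accrual would change it.

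At 85% true feasibility the probability of stage-1 rejection is 0.144 under either rule, so a promising regimen is no more likely to be rejected.

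**What to change.** 1. In 7.2.2 and 7.2.5, add: Enrolment stops and the stage-1 rejection applies as soon as the fifth of the first 19 evaluable patients meets the non-feasibility criterion.
2. Reconcile the 19 patients in 7.2.2 with the 10 in 7.2.5. The error rates reproduced above belong to a stage 1 of 19.
3. In 6.7, add: Sites notify every event that meets the DLT or non-feasibility definition promptly to the coordinating investigator, on the phone or fax route already used for SAEs, and the coordinating investigator keeps the running count.

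The cost is a few sentences and somewhat more notification work for sites. No patients are added, and type I error and power do not change. The change concerns enrolment and the existing rejection rule only; it alters no dose or treatment rule for patients already enrolled. The downside is that, if the trial stops early, the toxicity profile rests on fewer than 19 patients.
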